In the equations above [Eq 3c] and [Eq 4c], X_i are facility-level variables intended to proxy for the quality and size of each facility. We will include the following variables as control variables in our model:

- Mean availability of all medication surveyed (taking the mean across binary availability indicators for each medication surveyed)
- Number of health care providers for children under 5
- If healthy facility has a functional stethoscope
- If health facility is connected to the electricity grid
- If healthy facility provides oxygen therapy

Fixed Effects

The primary paired outcomes analysis model [Eq 3a] includes facility category fixed effects. We will also report the results of running the model with alternate fixed effects:

1. Individual facility fixed effects
2. Region fixed effects – this specification will be done removing the weighting specified in the *Analysis* section.
3. Sampling strata fixed effects

Technical Challenges

I. Multiple Hypothesis Testing

To account for the large number of hypotheses being tested in the analysis, we will adjust our results for multiple hypothesis testing by using the Holm-Bonferroni correction. This correction imposes a more conservative threshold for statistical significance since standard cutoffs would likely result in a statistically significant outcome by chance alone (i.e., false positive). This ensures that statistically significant findings are more likely to reflect actual change rather than a false positive.¹⁶

The Holm-Bonferroni correction is an extension of the popular Bonferroni correction, which very simply adjusts the threshold for significance by a factor equal to the number of tests being conducted. Instead of adjusting by a constant factor for all tests, the Holm-Bonferroni correction makes a sequential step-wise adjustment by increasing the threshold of the most significant result by a factor equal to the total number

¹⁶ If we do multiple comparisons, the probability of a false positive is: $1-(1-a)^m$, where m is the number of tests and a is the significance level (set at 0.05 by convention). For example, if we were to ask seven questions from the same data at the 5% level of significance, we would increase the chance of finding at least one false positive from 5% (with one question) to about 30%.

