of tests, the next most significant results with a factor equal to the total number of tests – 1, etc.¹⁷ The benefit of the Holm-Bonferroni test is that it accounts for outcomes that are dependent in a less conservative way than Bonferroni, thereby improving the statistical power of the test.¹⁸ For this correction, our “families” of hypotheses are as outlined in *Table 1*.

II. Missing Data

Missing values can take the form of non-response (e.g. uncompleted surveys), partial response (e.g. “Don’t know” responses), or errors in the data. Minor and random missing values can be omitted from the analysis. If we find that missing values are unexpectedly high, we may check the sensitivity of the complete case estimate using imputation methods to replace missing values. However, we expect minimal missing data since the digital survey form includes constraints that require data to be entered before the enumerator can proceed with data collection.

There are three main reasons a facility surveyed at baseline may not be surveyed in Phase II data collection rounds:

1. Temporary closures – In Phase I, Round 2, two facilities from the original sample were not surveyed due to temporary closures. These two facilities were reopened for Phase I, Round 3 surveying, but we may see other facilities drop from the Phase II sample for similar reasons.
2. Permanent closure – If a public health facility surveyed in Phase I has since closed, we will randomly select another public health facility of the same level from the same district not previously included in the study.
3. Inability to contact facility – Before the in-person round of Phase II was suspended, the survey teams visited 97 facilities of the 251 Phase II facilities and collected new contact information. The 154 remaining facilities will need to be contacted using phone numbers provided by the District Medical Officer (DMO) and phone numbers collected in Phase I. If these numbers are incorrect or outdated, we may not be able to contact the health facility. In this instance, we will randomly select another public health facility of the same level from the same district not previously included in our survey.

III. Evaluation Effects

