There is some risk of various evaluation effects (also known as observer, or Hawthorne, effects), the process by which a participant of a study changes their behavior due to the knowledge that they are under study and for what specific purpose. For example, healthcare workers may try to request (unnecessarily)

¹⁷ In practice, this is performed by sorting outcomes into groups called families whereby outcomes or tests within a family are correlated (dependent). Following outcome sorting, the change in the outcome across survey rounds is estimated using either model. Unadjusted p-values from each test within a family are then sorted in ascending order and corrected by multiplying the p-value of a given rank by $(m - n)$, where m is the total number of tests within a given family of related outcomes and n is the rank order of the p-value from 0 (smallest) to m (largest). If the adjusted p-value is less than 0.05, then that outcome is statistically different between rounds.

¹⁸ Abdi, H (2007). Bonferroni and Šidák corrections for multiple comparisons. *Encyclopedia of measurement and statistics*, 3, 103-107.

additional Amox-DT stock if they have knowledge that this is one of our primary outcomes – and especially if they discern that we think having Amox-DT stock is desirable. For these reasons, the survey tool contains additional questions about other treatments for childhood illnesses to lessen the likelihood that a healthcare worker will identify pneumonia and its associated treatments as being our major outcome of interest. By doing so, we also aim to decrease the risk of the observer effect influencing the quality of our data.

IV. Other Study Limitations

Additional limitations of this study are due to data sources, time constraints, and potential respondent biases.

These limitations include:

- The quality of the data differs based on the data source. The research team may be able to collect observable and verifiable data in some cases but will have to rely on respondent recall for others. For example, the research team may be able to verify if the medications were available in the stock rooms and dispensing outlets on the day of the visit. However, data on stock outs relies on a combination of records and recall, dependent on whether the respondent has records available for reference as well as the quality of those records.

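### Footnote 17 misstates Holm-Bonferroni: the rank range runs one too far and the step-down stop is missing; whether m counts the seven rounds also needs stating

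*Combined protocol and SAP*

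**What the plan says.** In Technical Challenges, section I (Multiple Hypothesis Testing), the authors write that "we will adjust our results for multiple hypothesis testing by using the Holm-Bonferroni correction". The body text describes a procedure that "makes a sequential step-wise adjustment by increasing the threshold of the most significant result by a factor equal to the total number" of tests, and "the next most significant results with a factor equal to the total number of tests – 1, etc". Taken as multipliers on the ordered p-values, these are m, m-1, ..., 1, which are Holm's factors.

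Footnote 17 turns this into a working rule. Unadjusted p-values in a family are sorted in ascending order and multiplied by (m - n). Here m is the number of tests in the family and n "is the rank order of the p-value from 0 (smallest) to m (largest"). An outcome is then called statistically different between rounds if its own adjusted p-value is below 0.05. The footnote has no instruction to stop at the first non-rejection and no requirement that adjusted values be non-decreasing. It says the change is estimated with either model.

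On scope, the families "of hypotheses are as outlined in" Table 1. That table groups metrics under availability and stocking and does not mention rounds. Elsewhere the plan covers seven remote rounds (Study Aims). It tests each Phase II round against Phase I, Round 1 (Analysis, Outcomes) on every Table 1 metric, under a paired and an unpaired specification (Analysis Description).

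**The concern.** Footnote 17 is the only place where the plan says how an outcome comes to be declared changed, so an analyst would code from it. It departs from the named method in two ways.

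- **Rank range.** Ranks 0 to m are m+1 ranks for m tests. At n = m the multiplier is zero, so the largest p-value in a family would become 0 and pass.
- **No step-down.** Because each adjusted value is judged alone, a larger p-value can be declared significant while smaller ones in the same family are not. Such a result is hard to defend and is not what Holm would give.

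A separate question is scope. The section sets out to deal with a large number of hypotheses, and repeating the tests over rounds is a main source of that number. The text does not say whether the rounds, or the two specifications, count towards m.

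**Working it through.** **1. The plan's own figure.** Footnote 16 gives the chance of at least one false positive as 1-(1-a)^m, where a "is the significance level (set at 0.05 by convention"). With a = 0.05 and m = 7: 1 - 0.95^7 = 0.302. This reproduces the stated figure of about 30 per cent.

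**2. Rank range.** Take m = 3 and p = 0.20, 0.60, 0.90.

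| Rule | Factors | Adjusted values |
|---|---|---|
| Footnote 17, largest p-value at rank m | 3, 2, 0 | 0.60, 1.20, 0 |
| Body text (ranks 0 to m-1) | 3, 2, 1 | 0.60, 1.20, 0.90 |
| Holm (running maximum, before capping at 1) | 3, 2, 1 | 0.60, 1.20, 1.20 |

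On the literal reading the outcome with p = 0.90 is declared. With ranks 0 to m-1 this disappears.

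**3. Missing stop.** Take m = 5 and ranks 0 to 4, so the factors are 5, 4, 3, 2, 1.

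| p | Factor | p × factor (footnote) | Running maximum (Holm) |
|---|---|---|---|
| 0.012 | 5 | 0.060 | 0.060 |
| 0.013 | 4 | 0.052 | 0.060 |
| 0.014 | 3 | 0.042 | 0.060 |
| 0.030 | 2 | 0.060 | 0.060 |
| 0.200 | 1 | 0.200 | 0.200 |

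The footnote declares only the third outcome; Holm declares none.

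**4. Does the missing stop inflate the error rate?** Without a stop, the k-th smallest p-value is declared if it is below 0.05/(m-k+1). Hochberg's step-up procedure uses the same thresholds and also declares everything with a smaller p-value. The footnote's declarations are therefore a subset of Hochberg's, and Hochberg controls family-wise error under independence and usual positive dependence. Simulation (two-sided normal tests, 400,000 replicates, all nulls true) agrees:

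| m | Correlation between outcomes | No stop | Holm |
|---|---|---|---|
| 3 | 0 | 4.94% | 4.91% |
| 3 | 0.5 | 4.56% | 4.48% |
| 5 | 0 | 4.93% | 4.93% |

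No scenario exceeded 5%, including those with some true effects.

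**5. Rounds.** Counting primary and secondary metrics, Table 1 has 3 for availability (4 if mean and median are separate) and 5 for stocking (7 with the context metrics). Suppose correct Holm at 5% is applied separately in each of seven rounds and all nulls are true. With independent rounds and exactly 5% in each, the chance of at least one false positive in a family is again 1 - 0.95^7 = 30.2%. The documents give no correlations, so those below are assumptions. The simulation used 200,000 replicates, and each cell shows m = 3 / m = 5.

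| Between-round correlation | Outcomes independent within a round | Outcomes correlated 0.5 |
|---|---|---|
| 0.3 | 27.5% / 27.8% | 25.1% / 24.1% |
| 0.5 | 24.0% / 24.6% | 21.7% / 21.1% |
| 0.7 | 19.2% / 20.0% | 17.0% / 16.5% |

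These are per-family figures. For one given outcome under the same per-round Holm, the chance over seven rounds is about 4% to 11% across the same settings.

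If rounds were placed inside the family, m would be 3 × 7 = 21 and 5 × 7 = 35. The first-step thresholds would fall from 0.05/3 = 0.0167 and 0.05/5 = 0.0100 to 0.05/21 = 0.00238 and 0.05/35 = 0.00143.

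**The case against.** The strongest reply is that the zero multiplier is a slip, not a rule anyone would run. If ranking starts at 0, m p-values end at rank m-1. The formula (m - n) then gives exactly the body text's factors. That stands: a reader might infer that the plan will declare the least significant outcome in every family, but the body text contradicts that. What remains is a contradiction between text and footnote that must be corrected.

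A second reply is that the missing stop does no harm to error control. On the error rate this also stands, as step 4 shows. A reader might infer that the promised 5% control fails, and the calculations do not support that. But the rule is neither Holm nor Hochberg. In the five-outcome example Hochberg would declare the first three (0.014 is below 0.05/3 = 0.0167), Holm none, and the footnote only the third. Holm's validity under arbitrary dependence is also lost, and the footnote itself describes tests within a family as dependent.

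A third reply is that the plan promises no error rate across rounds, and that footnote 16's example ("if we were to ask seven questions from the same data at the 5% level of significance") concerns seven questions, not seven rounds. Both are true, so a breach of stated control cannot be inferred. Whether repeated monitoring rounds form one family is a matter of judgement. The authors also name the ten-region weighted estimate as preferred and keep both specifications deliberately. None of this tells an analyst what m is or which model's p-values enter.

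Finally, the primary aim is to estimate levels with 95% confidence intervals, which the correction does not touch. This limits the reach of the point to the change-over-time comparisons.

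**Conclusion.** Footnote 17 is wrong as written and should be replaced. The rank range contradicts the body text, and the lack of a step-down stop can change which outcomes are declared and in what order. The consequence is a loss of coherence and of Holm's general guarantee. It is not a demonstrated inflation above 5%, provided the tests are independent or positively dependent in the usual way.

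The scope over rounds is a clarification and not a breach. With Holm applied separately per round, the chance of at least one false positive per family over seven rounds is about 19% to 28% for between-round correlations of 0.7 to 0.3 if outcomes are independent within a round. It is about 17% to 25% if they correlate 0.5. These figures assume that all nulls are true, that the correlations are as stated, and that there are 3 or 5 tests per family. The eighth, in-person round is left to a companion document and is not counted.

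**What to change.** Replace the rule in footnote 17 with the following. For p-values in a family sorted in ascending order, k = 1, ..., m, the adjusted value is p_adj(k) = min(1, max over i ≤ k of (m - i + 1) × p(i)). An outcome is declared statistically different if p_adj(k) is below 0.05. This matches the body text's factors and builds in the stop. It is a change of wording only.

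Add a statement on scope: how many tests each Table 1 family contains, which specification's p-values enter the correction, and whether m includes the seven rounds or control is claimed per round only. Any of these choices can be defended if stated in advance. Per-round control costs nothing beyond saying so. Including the rounds makes single-round claims harder to reach, with the first-step thresholds shown in the working. Neither change affects data collection or the estimates of levels.

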APPENDIX I: Data collection tools

Table A1: Public Facility Questionnaires Overview

Questionnaire	Purpose	Respondent	Contents
1. Facility questionnaire	
Attain consent to talk to healthy facility staff, to collect data remotely, and identify respondents for the remote data collection rounds.
 
Gather descriptive information about the facility (e.g. number of staff, availability of oxygen therapy, electricity supply).
	Facility in-charge	
 • Structured interview (approximately 15 minutes)
2. Respondent introduction questionnaire	
Introduce the remote data collection methodology and provide the instructions sheet on how to collect the medicine availability and stock levels of peds-Amox and other comparator medicines from facility dispensing outlets and stock rooms.
	
Staff member identified by the facility-in-charge as someone who is familiar with the availability and stocking of pediatric medications at the facility, typically the stock room in-charge or stock room attendant.
	
 • Structured interview (approximately 10 minutes)
3. Dispensing outlet and stock room questionnaire	
Understand availability of peds-Amox and other comparator medicines and stock levels of peds-Amox in the facility dispensing outlets and stock rooms.
	
Same staff member who participated in the respondent introduction questionnaire (questionnaire 2)
	
 • Structured interview (approximately 25 minutes) • Stock count (dispensing outlet and stock room)
